##### 2) KDQOL

Descriptive statistics of KDQOL should be calculated by subscale (Section 4.16 [Table 4.16.2] "subscale") for measured values and changes from the first day of the treatment period at each evaluation time point. Scores by subscale should be calculated using a scoring method (Section 4.16). A paired t-test should be performed for before and after comparison of changes in KDQOL from the first day of the treatment period.

LSMean, its standard errors, and 2-sided 95% CI should be calculated and shown for the change in KDQOL from the first day of the treatment period to each evaluation time point using the MMRM model (with compound symmetry [CS] for a covariance matrix within subject variance).

#### **8.5.4 Statistical issues**

##### **8.5.4.1 Adjustment for covariates**

In the analysis of efficacy, in order to consider the effect of the measurement value of the first day of the treatment period on the change of each measurement, the analysis using the MMRM model (with compound symmetry [CS] for a covariance matrix within subject variance) should be conducted using the measurement value of the first day of the treatment period as a covariate in the general analysis including the analysis of the primary endpoint.

**8.5.4.2 Handling of dropout or missing data**

Provided in 7. Data handling.

**8.5.4.3 Multicenter trial**

For FAS, the following analysis should be conducted for each following endpoint for each site. Descriptive statistics of Hb values should be calculated at Week 24 of the treatment period (imputed by the LOCF method).

Descriptive statistics should be calculated for the mean dose of the study drug at Week 20 to Week 24 of the treatment period. No analysis will be performed for each patient cohort.

**8.5.4.4 Subgroup analyses**

The following analyses should be conducted for subpopulations based on the stratification factor for each endpoint in the table below in the FAS. Unless otherwise specified, no analysis will be performed for individual patient cohorts.

(1) Hb value at Week 24 of the treatment period

LSMean, its standard error, and 2-sided 95% CI should be calculated using the MMRM (with compound symmetry [CS] for a covariance matrix within subject variance).

(2) Mean dosage of study drug at Week 20 to Week 24 of the treatment period

Descriptive statistics should be calculated.

(3) Responder rates at Week 24 of the treatment period

With respect to the responder rate at Week 24 of the treatment period (rate of subjects with increased Hb value by  $\geq 1.0$  g/dL from the first day of the treatment period), the number of responders, proportion, and 95% CI (Clopper-Pearson [Exact] method) for the proportion should be provided.

Only the Conversion (Hb value  $< 11.0$  g/dL) cohort should be analyzed.

(4) Target Hb value achievement rate at Week 24 of the treatment period

The number, proportion, and 95% CI (Clopper-Pearson [Exact]) method) for the proportion of subjects with Hb values within the target range (11.0 g/dL to  $< 13.0$  g/dL) should be provided.

Table 8.5.4.4.1 Subgroup analysis of efficacy

Endpoints	Stratification factor	Stratified category
1. Hb values at Week 24 of the treatment period 2. Mean dosage of study drug at Week 20 to Week 24 of the treatment period 3. Responder rates at Week 24 of the treatment period 4. Target Hb achievement rate at Week 24 of the treatment period	Sex	Male, Female
	Age at informed consent (years)	<65, ≥65
		<75, ≥75
	Body weight (body weight excluding dialysate weight) (kg)	<60, ≥60
	BMI (kg/m  ) on the first day of the treatment period	<25, ≥25
	Causative diseases of CKD	Diabetes, hypertension, autoimmune/glomerulonephritis/vasculitis, interstitial nephritis/pyelonephritis, cystic/hereditary/congenital disease, neoplasm/tumor
	Duration of nephrogenic anemia (years)	<1, 1 to <5, ≥5
	Complication	hypertension, diabetes, dyslipidemia
	Hb value (g/dL) on the first day of the treatment period	<9, 9 to <11, ≥11
	Liver function test (U/L) on the first day of the treatment period	AST and ALT both below the upper limit of normal, either above the upper limit of normal and both ≤ 2 times the upper limit of normal, either > 2 times the upper limit of normal
	CRP (mg/dL) on the first day of the treatment period	<0.31, ≥0.31
	Serum ferritin value (ng/dL) on the first day of the treatment period	Divide the number of subjects into three categories based on the tertile
	TSAT (%) on the first day of the treatment period	Divide the number of subjects into three categories based on the tertile
Smoking status	3 categories: Never Smoked, Ex-Smoker, Current Smoker	

	Administration of oral iron supplement on the first day of the treatment period	Yes or No
	Treatment with oral iron supplement at Week 24 of the treatment period	Yes or No
	Iron-containing phosphate binders on the first day of the treatment period	Yes or No
	Iron-containing phosphate binders at Week 24 of the treatment period	Yes or No
	Previous ESA formulation (Conversion cohort only)	Epoetin (epoetin alfa or epoetin beta), darbepoetin alfa, epoetin beta pegol, other
	Epoetin alfa or epoetin beta weekly dose (IU) (Conversion cohort only)	Divide the number of subjects into three categories based on the tertile
	Weekly dosage of Darbepoetin alfa ( $\mu\text{g}$ ) (Conversion cohort only)	Divide the number of subjects into three categories based on the tertile
	Weekly dosage of Epoetin beta pegol dose ( $\mu\text{g}$ ) (Conversion cohort only)	Divide the number of subjects into three categories based on the tertile
	CYP2B6 inducer coadministration *	Yes or No

\* List of CYP2B6 inducers obtained from The Metabolism and Transport Drug Interaction Database (DIDB®).

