#### 3.2 Inclusion criteria

Subjects must meet all inclusion criteria below and have capacity to grant informed consent. Laboratory tests to determine inclusion criteria will be performed at a central testing facility. If a given laboratory test is performed multiple times during the screening period, the most recent test will be used for determination.

- (1) Patients at least 20 years of age as of the day of consent (either sex)
- (2) Patients with CKD diagnosed according to the Japanese Society of Nephrology's "Clinical Practice Guidebook for Diagnosis and Treatment of Chronic Kidney Disease 2012" as of the day of consent.
- (3) Patients who have been receiving peritoneal dialysis for at least 4 weeks prior to the first day of the screening period, but excluding patients also receiving haemodialysis.
- (4) Patients expected to initiate haemodialysis during the treatment period.
- (5) Correction cohort: Patients who have not received erythropoiesis-stimulating agent (ESA) treatment from 8 weeks prior to the first day of the screening period. However, patients receiving ESA treatment at consent may join the study if they discontinue this treatment after consent and have a washout period of at least 8 weeks.

Conversion cohort Patients receiving the same formulation of ESA using the same administration route and the same dose interval (the dose interval should be the one described in the package insert for the ESA formulation) within 8 weeks prior to the first day of the screening period, using the dosages described below.

Dosage:

- ✓ Epoetin alfa (recombinant) and epoetin beta (recombinant)  $\leq 12,000$  IU every 2 weeks
- ✓ Darbepoetin alfa (recombinant):  $\leq 120$   $\mu$ g every 2 weeks

- ✓ Epoetin beta pegol (recombinant):  $\leq 250$   $\mu\text{g}$  every 4 weeks
- (6) Patients with the following mean Hb values during screening, using the mean of the latest two tests:
  - ✓ Correction cohort:  $\geq 8.0$  g/dL,  $< 11.0$  g/dL
  - ✓ Conversion cohort:  $\geq 9.0$  g/dL,  $< 12.5$  g/dL
- (7) Patients with a difference of  $< 1.5$  g/dL in Hb for the latest two tests in the screening period
- (8) Patients with serum ferritin values of  $\geq 100$  ng/mL or transferrin saturation (TSAT) of  $\geq 20\%$  during the screening period.
- (9) Patients with folic acid and vitamin B12 values above standard minimum values during the screening period.

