#### 3.2 Inclusion criteria

Subjects must meet all inclusion criteria below and have capacity to grant informed consent. Laboratory tests to determine inclusion criteria will be performed at a central testing facility. If a given laboratory test is performed multiple times during the screening period, the most recent test will be used for determination.

- (1) Patients at least 20 years of age as of the day of consent (either sex)
- (2) Patients with CKD diagnosed according to the Japanese Society of Nephrology's "Clinical Practice Guidebook for Diagnosis and Treatment of Chronic Kidney Disease 2012" as of the day of consent.
- (3) Patients who have been receiving peritoneal dialysis for at least 4 weeks prior to the first day of the screening period, but excluding patients also receiving haemodialysis.
- (4) Patients expected to initiate haemodialysis during the treatment period.
- (5) Correction cohort: Patients who have not received ESA treatment 8 weeks prior to the first day of the screening period. However, patients receiving ESA treatment at consent may join the study if they discontinue this treatment after consent and have a washout period of at least 8 weeks.

Conversion cohort: Patients receiving the same formulation of ESA using the same administration route and the same dose interval (the dose interval should be the one described in the package insert for the ESA formulation) within 8 weeks prior to the first day of the screening period, using the dosages described below.

Dosage:

- ✓ Epoetin alfa (recombinant) and epoetin beta (recombinant):  $\leq 12,000$  IU every 2 weeks
  - ✓ Darbepoetin alfa (recombinant):  $\leq 120$   $\mu$ g every 2 weeks
  - ✓ Epoetin beta pegol (recombinant):  $\leq 250$   $\mu$ g every 4 weeks
- (6) Patients with the following mean Hb values during screening, using the mean of the latest two tests:
    - ✓ Correction group:  $\geq 8.0$  g/dL,  $< 11.0$  g/dL
    - ✓ Conversion group:  $\geq 9.0$  g/dL,  $< 12.5$  g/dL
  - (7) Patients with a difference of  $< 1.5$  g/dL in Hb for the latest two tests in the screening period
  - (8) Patients with serum ferritin values of  $\geq 100$  ng/mL or transferrin saturation (TSAT) of  $\geq 20\%$  during the screening period.

- (9) Patients with folic acid and vitamin B12 values above standard minimum values during the screening period.

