## 6. Patient Cohorts

The patient cohorts are defined below. Each patient cohort should be analyzed as needed.

Correction cohort: A group of patients who have not received ESA formulations from 8 weeks prior to the first day of the screening period.

Conversion cohort: A group of patients who have received ESA formulations from 8 weeks prior to the first day of the screening period.

Conversion (Hb value  $\geq 11.0$ ) cohort: A subset of patients in the Conversion cohort whose mean Hb value during the last 2 screening sessions is  $\geq 11.0$  g/dL.

Conversion (Hb value  $< 11.0$ ) cohort: A subset of patients in the Conversion cohort whose mean Hb value during the last 2 screening sessions is  $< 11.0$  g/dL.

As the number of patients in the Correction cohort is small, only the individual time course diagram of Hb values will be prepared.

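### In SAP Table 8.5.4.4.1 the Week 24 responder rate is stratified by the same first-day Hb that is subtracted to define response, so regression to the mean tilts it downward across the strata (minor)

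*SAP*

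**What the plan says.** SAP 8.5.4.4 (3) defines the responder rate: "With respect to the responder rate at Week 24 of the treatment period (rate of subjects with increased Hb value by" at least 1.0 "g/dL from the first day of the treatment period), the number of responders, proportion, and 95% CI". Hb on the first day of the treatment period (Day-1 Hb below) is therefore the value subtracted. The result is a crude proportion with a Clopper-Pearson interval.

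The population is restricted: "Only the Conversion (Hb value" <11.0 g/dL) cohort is analysed. SAP section 6 defines that cohort as "A subset of patients in the Conversion cohort whose mean Hb value during the last 2 screening sessions is" below 11.0 g/dL. Protocol 3.2 (6) sets the entry limits on the same quantity: "Patients with the following mean Hb values during screening, using the mean of the latest two tests", with a floor of 9.0 g/dL for conversion patients.

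On the subgroups, the SAP says: "The following analyses should be conducted for subpopulations based on the stratification factor for each endpoint in the table below in the FAS". Table 8.5.4.4.1 sets one list of factors against all four endpoints, the responder rate included. One factor is "Hb value (g/dL) on the first day of the treatment period", cut at <9, 9 to <11 and ≥11.

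The errata to the SAP correct the CYP2B6 row of this table and leave the Hb row as it is. The Day-1 covariate in the SAP section on adjustment for covariates belongs to the MMRM analyses and does not reach a crude proportion.

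**The concern.** One measurement does two jobs. A subject whose Day-1 Hb is low by chance drops into a low stratum and also needs less to show a 1.0 g/dL rise. A chance high does the reverse. The rate is then expected to fall from <9 to ≥11 with no drug effect, or with the same effect in everyone.

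The cohort restriction sharpens this, because subjects reach the outer strata only by a Day-1 departure from their screening mean. The study is uncontrolled, so no second arm would show the same slope for comparison. A reader could take the row to mean that the drug works best in the most anaemic patients and hardly at all from 11 g/dL upward.

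**Working it through.** **The plan's own figures.** The documents give no responder rate by stratum to reproduce. The only design figure is the precision of mean Hb: t(0.975, 39) × 1.78/√40 = 0.569, which matches the stated ±0.57 g/dL. The 1.78 describes the spread of Hb across subjects, so it cannot serve as the within-subject SD needed here.

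**Step 1: who can be in each stratum (from the definitions alone).** The screening mean is at least 9.0 (Protocol 3.2 (6)) and below 11.0 (SAP section 6).
- Day-1 Hb <9 means Day-1 Hb is below the subject's own screening mean.
- Day-1 Hb ≥11 means Day-1 Hb is above it.

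The ≥11 stratum is expected to be populated: SAP 8.5.1 (4), on days to reach target, analyses this same cohort and has to exclude subjects with Day-1 Hb of 11.0 or more.

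**Step 2: the coupling in one formula.** Let T be a subject's true Hb, unchanged over the study, and let e1 and e24 be independent errors with SD s at Day 1 and Week 24. Response means e24 − e1 ≥ 1.0, so

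P(response given e1) = 1 − Φ((1.0 + e1)/s).

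At s = 0.6:
- e1 = −0.6: 1 − Φ(0.67) = 25%
- e1 = 0: 1 − Φ(1.67) = 4.8%
- e1 = +0.6: 1 − Φ(2.67) = 0.4%

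**Step 3: rates by Day-1 stratum.** Simulation, 4 million draws per setting. Assumed: T ~ N(10.9, 0.9); two screening values, Day 1 and Week 24 each equal T plus independent error of SD s; subject kept if the screening mean is 9.0 to <11.0; no true change.

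| s (g/dL) | <9 | 9 to <11 | ≥11 | Share of cohort in <9 | Share in ≥11 |
|---|---|---|---|---|---|
| 0.3 | about 6% | 1% | 0% | 1.8% | 12% |
| 0.4 | 19% | 4% | 0.2% | 2.6% | 16% |
| 0.6 | 44% | 13% | 1.5% | 5% | 23% |
| 0.8 | 57% | 21% | 3.5% | 8% | 28% |

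With a uniform true rise of 0.6 g/dL and s = 0.6, the rates are 74/36/9%. The further entry limit in Protocol 3.2 (7), a difference below 1.5 "g/dL in Hb for the latest two tests in the screening period", barely moves these figures.

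**Step 4: the same subjects stratified by screening mean.** The screening values do not enter the change. With no true change the rate is therefore 1 − Φ(1.0/(√2 × s)) in every stratum; at s = 0.6 that is 1 − Φ(1.18) = 11.9%. With the uniform 0.6 rise it is 1 − Φ(0.4/0.849) = 31.9%. The simulation gives the same values for <10 and ≥10.

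**Step 5: a common target.** Suppose instead that dosing brings everyone to a Week 24 Hb of N(11.5, 0.9), independent of baseline (assumed; s = 0.6). The rates by Day-1 stratum are then 98/63/16%. By screening mean they are 71% (<10) and 47% (≥10), so a gradient remains.

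**Step 6: stratum sizes.** For an assumed 20 subjects in this cohort, <9 holds 20 × 1.8% to 20 × 8%, or 0.4 to 1.6 subjects. The ≥11 stratum holds 20 × 12% to 20 × 28%, or 2.4 to 5.6.

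**The case against.** **A gradient is expected anyway.** The dose algorithm steers every subject towards 11.0–13.0 g/dL, raising the dose below 11.0 and lowering it above 12.5. Those who start lower have further to rise, and those already at 11 or more have little room for a 1.0 g/dL gain. This stands. Step 5 shows that a gradient survives under the screening mean.

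**Day-1 departures are not all chance.** Up to 6 weeks may separate the first screening day from the first treatment day, and conversion patients may stay on ESA until then. Some of the movement may be real and lasting, and that part does not regress. This stands too, and it makes the size uncertain. So does the unknown within-subject SD: at 0.3 the fall is only about 6 percentage points.

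**The table could hardly show the effect.** With about one subject in <9, the exact interval the SAP requires would be nearly uninformative (0 to 97.5% for 0 of 1). No interaction test is planned, and the same row reports Week 24 Hb, dose and target achievement, none of which subtracts Day-1 Hb. This limits the harm.

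None of this removes the coupling. Its direction is built in, and neither the errata nor the covariate rule addresses it.

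**Conclusion.** The point holds as a minor one. For the responder rate, Day-1 Hb is both stratifier and subtrahend, and the outer strata are made up entirely of subjects whose Day-1 value left their screening mean. That much follows from the text. The size rests on assumptions the documents cannot confirm: a true Hb of N(10.9, 0.9), independent errors, and a within-subject SD between 0.3 and 0.8 g/dL. Over that range the no-change rate in <9 runs from about 6% to 57%, against 0% to 3.5% in ≥11.

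A reader might infer more, and the documents do not support it:
- That any observed gradient is pure artefact. Treatment to one target range gives a second reason for it.
- That changing the stratifier would make the rates flat. That is true only with no change or a uniform change.
- That the trial's main result is biased. The primary analysis does not use this table, which is descriptive.

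**What to change.** In Table 8.5.4.4.1, for endpoint 3 only, replace Day-1 Hb as the stratification factor with the mean of the last two screening Hb values, cut for example at <10 and ≥10 g/dL. That mean is already needed for inclusion (6) and for the cohort split, and it does not enter the change. The one exception is a subject whose Day-1 Hb is missing: SAP 7.4 then takes the nearest value, which could be a screening value. Keep Day-1 Hb as the factor for endpoints 1, 2 and 4.

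Add a footnote that a gradient by starting Hb may remain because all subjects are dosed towards one target range, so it should not be read as a differential drug effect.

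The cost is one line of SAP wording, one footnote and one table re-run. The row has two strata instead of three. The change removes the Day-1 noise artefact but not the gradient that comes from the common target.

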#### 8.5.4.1 Multiple comparison and multiplicity

In this study, no multiplicity problem occurs.

## 8.6 Safety analysis

The safety analysis population should be analyzed. When necessary, frequency and proportion should be calculated for discrete variables and descriptive statistics for continuous variables. Unless otherwise specified, no analysis will be performed for each patient cohort.

### 8.6.1 Adverse events and adverse drug reactions

#### 8.6.1.1 Summary of adverse events and adverse drug reactions

The number (number of subjects with adverse events) and proportion of subjects in whom the following adverse events are observed at least once after the administration of the study drug to the end of the follow-up period should be calculated.

- Adverse event
- Adverse drug reaction
- Serious adverse event
- Serious adverse drug reaction
- Adverse event leading to discontinuation
- Adverse events leading to dose reduction or interruption of study drug
- Adverse events resulting in death (adverse event leading to death)

#### 8.6.1.2 Individual adverse events

For adverse events, adverse drug reactions, serious adverse events, non-serious adverse events, serious adverse drug reactions, adverse events leading to discontinuation, adverse drug reactions leading to discontinuation, adverse events leading to dose reduction or interruption of the study drug, adverse events leading to death, and adverse events leading to death, the number of subjects with individual adverse events classified by SOC and PT in MedDRA/J 20.1 (hereinafter the same) and the incidence should be calculated. The SOC is shown in the order of international consensus, and the PT is shown in descending order of the number of subjects with events (if the number is the same, ascending order of PT Code).

#### 8.6.1.3 Adverse events by severity

The number of subjects and incidence rate should be calculated for adverse events and adverse drug reactions by severity for the overall and for individual events classified by SOC and PT.

The tabulation method by severity (severe, moderate, mild) is as follows.

- (1) When adverse events of different severity occur in the same subject  
The most severe adverse event should be counted as 1 subject.
- (2) When multiple adverse events with the same degree occur in the same subject  
The same severity should be counted as 1 subject.
- (3) When multiple same adverse events occur in the same subject  
The adverse event with the highest severity should be counted as 1 subject.

**8.6.1.4 Adverse events by onset**

The number and incidence rate of subjects with adverse events and adverse drug reactions should be calculated for adverse event and adverse drug reaction by time of onset (every 12 weeks) for the overall and for individual events classified by SOC and PT. For the calculation of the incidence rate, the number of subjects at each evaluation time point is used as the denominator. (Tabulation unit: from the first day of the treatment period [Day 1] to Day 84, and Day 85 or after)

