#### 9.2.4.2 Adverse events

AEs are all clinically problematic or unplanned signs (including clinically significant abnormal laboratory values), symptoms, or illnesses occurring after administration of the study drug during the safety evaluation period, regardless of causal relationship with the study drug. Instances of aggravation of events (in terms of severity or seriousness) are treated as new AEs.

However, AEs occurring from informed consent to the first day of the treatment period which match criteria for serious adverse events are still reported to the study sponsor according to “11.1 Responses to Occurrence of Serious Adverse Events.”

(1) Symptoms and diseases

Investigators/subinvestigators will confirm AEs through interviews and examinations.

(2) Objective findings

Objective findings determined clinically problematic abnormalities\* by investigators/subinvestigators are treated as AEs.

\*Clinically problematic abnormalities are determined according to the following criteria.

- If related to clinical signs or symptoms.
- However, if the sign or symptom has already been separately reported as an AE, the relevant laboratory test abnormality does not require treatment as adverse event.
- If the relevant laboratory test abnormality was treated medically or surgically.
- If the relevant laboratory test abnormality causes a change in method of administration of the study drug (dosage change, drug holiday, discontinuation, etc.).
- If investigators/subinvestigators otherwise determine the abnormality to be clinically problematic.

(3) Adverse event evaluation and standards

1) Date of onset

Date the symptom or laboratory test abnormality was observed.

2) Severity

Adverse event severity is classified as follows:

1. Mild: No effect on activities of daily life
2. Moderate: Moderate impairment of activities of daily life caused by event
3. Severe: Event prevents performing activities of daily life

3) Seriousness

AE seriousness is classified as follows:

1. Not serious: Any events other than 2 below.
2. Serious: Any events (a) to (f):
  - (a) Fatal
  - (b) Life-threatening
  - (c) Necessitating hospitalization or prolongation of hospitalization for treatment
  - (d) Events leading to permanent or clear dysfunction or disability
  - (e) Other events or reactions judged medically significant
  - (f) Causing congenital anomalies or defects

4) Causal relationship with the study drug

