The investigator/subinvestigator will assess whether or not there is a logical possibility that the study drug caused the AE. This assessment will take into account factors not related to the study drug, including risk factors such as natural course and concurrent treatments for underlying or concomitant diseases, as well as the temporal relationship between the study drugs and the event (recurrence after resuming administration, elimination after discontinuation, etc.). AEs for which a logical possibility exists for causal relationship with the study drug are treated as ADRs.

1. Logical possibility
2. No logical possibility

5) Outcome

AE outcomes are classified as follows:

1. Recovery
2. Relief

3. Not recovered
4. Recovered with sequelae
5. Death
6. Unknown

6) Date of outcome

Date of outcome is determined according to the following criteria:

Recovery: Date of recovery. If date of recovery is not known, use date on which recovery was confirmed or determined.

Relief: Date on which relief was confirmed or determined.

Not recovered: Date on which “not recovered” was confirmed or determined.

Recovered with sequelae: Date on which “recovered with sequelae” was confirmed or determined.

Death: Date of death. If date is not known, use date of confirmation or determination.

Unknown: Date of death if outcome is unknown due to death of subject for cause other than the relevant AE. For other circumstances use date of confirmation or determination.

7) Action taken with the study drug

[figure not shown]
Actions taken with the study drug are classified into the following six categories:

1. Discontinuation of administration (study withdrawal)
2. Drug holiday
3. Dosage increase
4. Dosage reduction
5. No action
6. Not applicable (occurred after final administration of study drug)

8) Action taken other than with the study drug

Actions taken other than with the study drug are classified into the following two categories: If actions other than with the study drug were taken, details of these will be investigated and recorded in the CRF.

1. No
2. Yes

- Period [1] above is the 14 days from the day after completion of the treatment period, during which any AEs will be investigated.
- Period [2] above is the 28 days from the day after completion of the follow-up observation period; it is the period for follow-up investigations of AEs occurring during the safety evaluation period (treatment period + Period [1]).

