**8.6.1.5 Adverse events by dosage immediately before onset**

The number and incidence rate to total exposure period of adverse events and adverse drug reactions in overall and individual events classified by SOC and PT should be calculated by dose immediately before onset\*. The total exposure period is defined as the total number of days (days) that each dose was administered during the study period.

\*The tabulation unit by dose immediately before onset should be as follows:

MT-6548 group: daily dose (tabulation unit: 0 mg, 150 mg, 300 mg, 450 mg, 600 mg)

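### The late unit of the 12-weekly AE onset table has no end and takes in follow-up, so it is about 98–99 days against 84, with no correction for length (minor)

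*SAP*

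**What the plan says.** SAP 8.6.1.4 presents AEs and adverse drug reactions "by time of onset (every 12 weeks"), overall and by SOC and PT. The units are then specified: "Tabulation unit: from the first day of the treatment period [Day 1] to Day 84, and Day 85 or after". The second unit has no closing day. For the incidence, "the number of subjects at each evaluation time point is used as the denominator".

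8.6.1.4 does not restate the period over which AEs are collected. SAP 8.6.1.1 does: it counts subjects with an event "at least once after the administration of the study drug to the end of the follow-up period". The protocol agrees. Section 9.2.4.2 defines AEs as those "occurring after administration of the study drug during the safety evaluation period", and makes that period the treatment period plus Period [1]: "Period [1] above is the 14 days from the day after completion of the treatment period, during which any AEs will be investigated".

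No AE section of the SAP ends the late unit at Week 24 or shows follow-up separately in this table. The errata correct 8.6.1.2 but leave 8.6.1.4 as it was.

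**The concern.** A table by onset is read for one purpose: to see whether events become more or less frequent as treatment continues. That reading needs units of equal length, or a denominator that allows for unequal length. The label promises equal 12-week units. The definition gives one unit of exactly 12 weeks and one that runs on through follow-up, and a head count cannot correct for this.

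The study is uncontrolled, so no comparator arm would show the same artefact and expose it. A reader who sees a higher late percentage has nothing in the table to indicate that part of it may come from the longer unit. At stake is the interpretation of a secondary safety display, not an efficacy conclusion.

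**Working it through.** **Inputs from the documents**
- Unit width: 12 weeks (SAP 8.6.1.4).
- Week 24 visit: Day 168, permitted Day 161–175, with the first day as Day 0 (Protocol Table 9.1-1). The SAP calls the first day Day 1, so the same visit is Day 169, permitted Day 162–176.
- Last dosing day: the day before Week 24 (Protocol 8.4).
- AE follow-up: 14 days (Protocol 9.2.4.2).
- Planned size: 40 subjects (Protocol 6.1).

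**Assumptions not in the documents**
- A constant AE hazard, first taken to continue unchanged through follow-up and then relaxed.
- Dropout of 0% to 40% over 24 weeks.

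**Step 1: the plan's own figure.** 12 × 7 = 84 days, which reproduces Day 1 to Day 84.

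**Step 2: length of the late unit for a completer.** Length = Week 24 day + 14 − 84.
- SAP numbering: 169 + 14 − 84 = 99 days; 99/84 = 1.18.
- Week 24 taken as Day 168, as the fixed 28-day last interval in SAP 4.10 implies: 168 + 14 − 84 = 98 days; 98/84 = 1.17.
- Extremes: 161 + 14 − 84 = 91 days (ratio 1.08) to 176 + 14 − 84 = 106 days (ratio 1.26).

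On the nominal schedule in SAP numbering, dosing runs to Day 168. Each unit then holds 84 dosing days (1–84 and 85–168), and the 15-day surplus is entirely off drug. If the Week 24 visit is late, part of the surplus is on drug.

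**Step 3: effect on a percentage.** If a proportion *p* has an event in 84 days, the proportion in *L* days at the same hazard is 1 − (1 − *p*)^(*L*/84).

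| Early (84 days) | Late, 98 days | Late, 99 days | Subjects of 40, early → late |
|---|---|---|---|
| 10% | 11.6% | 11.7% | 4.0 → 4.6–4.7 |
| 20% | 22.9% | 23.1% | 8.0 → 9.2–9.3 |
| 60% | 65.7% | 66.0% | 24.0 → 26.3–26.4 |
| 90% | 93.2% | 93.4% | 36.0 → 37.3 |

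The relative excess is largest for rare events and small for common ones.

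**Step 4: a lower off-drug rate.** At half the on-drug rate, 14 follow-up days count as 7: 1 − 0.9^(91/84) = 10.8%, and 1 − 0.8^(91/84) = 21.5%. At a zero off-drug rate the exponent is 84/84 and the excess vanishes.

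**Step 5: dropout.** I simulated a constant dropout hazard, with 14 days of follow-up after stopping and a 98-day late unit.
- Late denominator = subjects on treatment at Week 12: with 10% to 40% dropout, the late/early ratio stays between 1.10 and 1.15 for *p* = 10% to 40%. Steady dropout does not cancel the effect.
- Late denominator = the Week 24 count: at *p* = 20% and 20% dropout, the table would show 24.5% late against 19.3% early with no true change. The unnamed time point therefore matters.
- Cancellation needs dropout confined to the late unit. A subject stopping at a uniform time there loses 42 days on average, so 42*f* = 14 gives *f* = one third of subjects.

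**Step 6: after the fix.** With the second unit closed at Week 24 (84 days), a constant rate of 20% gives 20% in both, 8 of 40 each. Event rates also agree over the open unit: 12 events in 84 days and 14 in 98 are both 1 per 7 days.

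**The case against.** The effect is small against sampling error. For 4 of 40 the exact 95% interval is 2.8% to 23.7%, and for 8 of 40 it is 9.1% to 35.6%. The shift in Step 3 is about one subject. The open boundary is printed in the tabulation unit, no test compares the two units, and following AEs off drug is deliberate: Protocol 5.2 sets the two weeks with the drug's half-life in mind. No document supports an off-drug AE rate equal to the on-drug rate, and for adverse drug reactions, also in this table, that assumption is weakest. All of this stands. It limits the size and severity of the point but does not make the units comparable.

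Four stronger readings are tempting, and the documents do not support them.
- *Post-treatment events are attributed to treatment.* An onset table assigns time, not cause. Causality is judged separately by the investigator (Protocol 9.2.4.2, SAP 4.12).
- *Only the late unit mixes on-drug and off-drug time.* A subject who stops by about Day 70 has follow-up inside the first unit. The late unit holds most follow-up time, not all.
- *A subject who stops in Days 71–84 and has an event after Day 84 must be missing from the late denominator.* 8.6.1.4 does not limit the denominator to subjects still on treatment. If it means subjects under observation, there is no mismatch. What can be said is that the time point is not named.
- *The by-dose table in SAP 8.6.1.5 sets follow-up events against a dose with no matching exposure.* That table has a 0 mg row, and "The total exposure period is defined as the total number of days (days) that each dose was administered during the study period", where the study period is defined as running to the last day of follow-up. Off-drug events and off-drug days can both fall in that row. The section does not say that they do, so a clarification is the most that is warranted.

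**Conclusion.** The point holds as a minor one. A table labelled as 12-weekly compares 84 days with about 98–99 for a completer (91–106 over the visit window), and a subject count does not correct for it. The reading that follow-up is included rests on the open second unit together with SAP 8.6.1.1 and Protocol 9.2.4.2, which agree.

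The apparent late rise depends on events continuing off drug. At an unchanged rate it is at most about 17–18% relative for rare events on the nominal schedule and about 4% for an event affecting 90% of subjects. It falls to nothing if no events arise off drug. The undefined denominator can add to it, depending on the time point chosen. A reader might infer that the plan would manufacture a late safety signal, but an excess of about one subject in 40, in a descriptive table, does not support that.

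**What to change.** In SAP 8.6.1.4, replace the two units with three:

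1. Day 1 to Day 84, on treatment.
2. Day 85 to the end of the treatment period.
3. Post-treatment follow-up, as a separate column that takes every subject's follow-up, including that of subjects who stop early.

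State that the denominator is the number of subjects entering each window. Print person-days, or events per 100 person-days, beside each percentage. The person-days also cover what closing the window does not: Week 24 visits away from the nominal day, and dropout within a window.

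In SAP 8.6.1.5, add one sentence saying whether post-treatment AEs and follow-up days both go in the existing 0 mg row.

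The cost is one more column and sparser cells. Onset dates, first and last dosing dates and visit dates are already collected, and the CRF action category already identifies events after the final dose. If the data are locked, Protocol 13.4 allows the table to be added with its reason given and the result kept distinct from the planned output.
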